9.3. Populations for Analyses

The primary analysis of efficacy will be based on the intent-to-treat (ITT) population that includes all randomized (Part 1) and all enrolled (Part 2) participants. Selected efficacy endpoints will also be performed on the efficacy-evaluable population that includes all ITT participants who have baseline and at least one post-baseline disease evaluation. Safety will be evaluated on the safety population that includes all participants who have received at least 1 dose of study intervention. The pharmacokinetic analyses will be performed on the pharmacokinetic evaluable population.

9.4. Statistical Analyses

9.4.1. Efficacy Analyses

Binary endpoints will be summarized with number and percentage of participants achieving the endpoint along with the corresponding 2-sided 95% exact confidence interval. These endpoints include CR, CR + CRh, CR+CRh+CRi, CR without MRD, MRD negativity, and transfusion independence. Hypothesis testing for the primary endpoint of CR rate will be performed using the Wilson Score test without continuity correction against the null hypothesis of 20% at the planned interim and final analyses (see Section 9.5, Interim Analysis).

The Kaplan-Meier method will be used to summarize time-to-events endpoints, including time to CR, time to CR + CRh + CRi, duration of CR, duration of CR+ CRh + CRi, PFS, and OS. Time to and duration of response are defined only for participants who achieved such responses; PFS and OS are defined for all participants. Duration of transfusion independence will also be summarized for participants who achieved such status.

No formal hypothesis testing or formal statistical comparison between the 2 dose groups is planned for study Part 1.

9.4.2. Safety Analyses

Adverse Events

The verbatim terms used in the eCRF by investigators to identify adverse events will be coded using the Medical Dictionary for Regulatory Activities (MedDRA). Toxicities will be graded for severity according to NCI-CTCAE, version 5.0. Intervention-emergent adverse events are adverse

events with onset during the intervention phase or that are a consequence of a pre-existing condition that has worsened since baseline. All reported adverse events will be included in the analysis. For each adverse event, the percentage of participants who experience at least 1 occurrence of the given event will be summarized by intervention group. In addition, comparisons between intervention groups will be provided if appropriate.

Specifically, the following will be summarized:

- All adverse events;
- Grade 3 or higher adverse events;
- Serious adverse events;
- Adverse events leading to discontinuation of treatment;
- Adverse events leading to death; and
- Adverse events of special interest.

Summaries, listings, datasets, or participant narratives may be provided, as appropriate, for those participants who die, who discontinue intervention due to an adverse event, or who experience a severe or a serious adverse event.

Parameters with predefined National Cancer Institute Common Terminology Criteria for Adverse Events (NCI-CTCAE) toxicity grades will be summarized. Change from baseline to the worst adverse event grade experienced by the participant during the study will be provided as shift tables.

Clinical Laboratory Tests

Laboratory data will be summarized by type of laboratory test. Reference ranges and markedly abnormal results (specified in the Statistical Analysis Plan) will be used in the summary of laboratory data. Descriptive statistics will be calculated for each laboratory analyte at baseline. Parameters with predefined NCI-CTCAE toxicity grades will be summarized. Change from baseline to the worst adverse event grade experienced by the participants during the study will be provided as shift tables.

Electrocardiogram (ECG)

Electrocardiogram data will be presented by descriptive analysis only.

Physical Examination

Clinically significant abnormal physical examination changes will be recorded and summarized as adverse events.

9.4.3. Other Analyses

A Data Review Committee (DRC) will be established as noted in Committees Structure in Appendix 3 Section 10.3 Regulatory, Ethical, and Study Oversight Considerations.

Pharmacokinetic Analyses

A snapshot date for PK samples to be analyzed will be defined, if required. Samples collected before this date will be analyzed for cusatuzumab and included in the population PK analysis. Samples collected after the snapshot date will be analyzed at a later date and may be included in a population PK re-analysis when they become available after database lock.

Data will be listed for all participants with available serum concentrations per intervention group. Participants will be excluded from the PK analysis if their data do not allow for accurate assessment of the PK (eg, incomplete administration of the study intervention; missing information of dosing and sampling times; concentration data not sufficient for PK parameter calculation).

All concentrations below the lowest quantifiable concentration or missing data will be labeled as such in the concentration database. All participants and samples excluded from the analysis will be clearly documented in the study report.

For each intervention group, descriptive statistics, including arithmetic mean, SD, coefficient of variation, median, minimum, and maximum will be calculated for all individual derived PK parameters including exposure information of cusatuzumab.

All serum concentrations below the lowest quantifiable concentration or missing data will be labeled as such in the concentration data presentations or SAS dataset. Concentrations below the lower quantifiable concentration will be treated as zero in the summary statistics. All participants and samples excluded from the analysis will be clearly documented in the Clinical Study Report.

Descriptive statistics will be used to summarize cusatuzumab serum concentrations at each sampling time point and PK parameters of cusatuzumab: C_{\min} and C_{\max} . Other PK parameters, including but not limited to $AUC_{(t_1-t_2)}$, $t_{1/2}$, CL, and V, when available, will also be summarized.

Mean and or median serum cusatuzumab concentration time profiles will be plotted after the first dose of study intervention, and individual serum concentration time profiles may also be plotted.

If sufficient data are available, population PK analysis of serum concentration-time data of cusatuzumab will be performed using nonlinear mixed effects modeling. Data may be combined with those of other selected studies to support a relevant structural model. Available baseline participant characteristics (demographics, laboratory variables, genotypes, race, etc.) will be tested as potential covariates affecting PK parameters. Details will be given in a population PK analysis plan and the results of the population PK analysis will be presented in a separate report. Exposure-response analyses may also be performed; if performed, details will be provided in a separate analysis plan and report.

Biomarker Analyses

The biomarker measures will be listed, tabulated, and where appropriate, plotted. Participants may be grouped by dose, or clinical endpoints. Analyses may be stratified by clinical covariates or molecular subgroups using the appropriate statistical methods (eg, parametric or non-parametric, univariate or multivariate, analysis of variance [ANOVA], or survival analysis, depending on the

endpoint). Correlation to clinical response may be explored to identify markers predictive of response (or resistance) to cusatuzumab and azacitidine combination treatment.

Results of biomarker analyses may be presented in a separate report. Planned analyses are based on the availability of clinically valid assays and may be deferred if emerging study data show no likelihood of providing useful scientific information.

Immunogenicity Analyses

The incidence of anti-cusatuzumab antibodies will be summarized for all participants who receive at least 1 dose of cusatuzumab and have appropriate samples for detection of antibodies to cusatuzumab (ie, participants with at least 1 sample obtained after their first dose of cusatuzumab).

A listing of participants who are positive for antibodies to cusatuzumab will be provided. The maximum titers of antibodies to cusatuzumab will be summarized for participants who are positive for antibodies to cusatuzumab.

The incidence of neutralizing antibodies (NAbs) to cusatuzumab will be summarized for participants who are positive for antibodies to cusatuzumab and have samples evaluable for NAbs to cusatuzumab.

Other immunogenicity analyses may be performed to further characterize the immune responses that are generated.

Pharmacodynamic Analyses

The pharmacodynamic biomarker measures will be listed, tabulated, and where appropriate, plotted. Changes in sCD27, blasts, LSCs, or gene expression over time from baseline will be summarized for groups by dose, or clinical endpoints.

Patient-Reported Outcomes

Total and subscale scores from the PRO instruments listed in Section 8.1 will be analyzed: EQ-5D-5L utility score, EQ-5D-VAS score, FACT-Leu Total, PWB, SWB, EWB, FWB, FACT-G, FACT-LeuS, FACT-Leu TOI.

For each scale score descriptive statistics (mean, standard deviation, median, and range) will be calculated for each assessment time point, for change from baseline at each time point, and for change from previous time point.

Mixed-model repeated measures will be used for longitudinal analyses of PRO score change over time for each subscale. Time-to-event analyses will also be conducted using the Kaplan-Meier method using specified MID thresholds to define time-to-worsening and time-to-improvement for each PRO scale score.

Medical Resource Utilization Analyses

Medical resource utilization will be descriptively summarized by intervention group.

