2.3. Study Day and Relative Day

Study Day 1 is the day of randomization for participants randomized in Part 1. By convention, 1 month equals to 30.4375 days, and 1 year equals to 365.25 days. Duration in days between 2 time points will be calculated as (end date – start date + 1).

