2.4. Baseline

Baseline value is defined as the last non-missing value collected on or before study Day 1.

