6. PATIENT-REPORTED OUTCOMES (PRO)

Patient-reported outcome instruments included in this study are the Functional Assessment of Cancer Therapy – Leukemia (FACT-Leu) and EuroQoL 5 Dimension 5 Level questionnaire (EQ-5D-5L).

The FACT-Leu is a 44-item instrument measuring health-related quality of life concepts. It is comprised of 4 subscales that make up the FACT-G: physical well-being (PWB, 7 items), social/family well-being (SWB, 7 items), emotional well-being (EWB, 6 items), and functional well-being (FWB, 7 items) and a fifth subscale for leukemia-specific concerns (LeuS, 17 items). Items are rated on a response scale from 0 (not at all) to 4 (very much). A Trial Outcome Index (FACT-Leu TOI) score can also be calculated by combining the FACT-PWB, FACT-FWB, and FACT-LeuS subscales. Subscale and total scores will be calculated according to instrument administration and scoring guidelines; higher scores indicate better health-related quality of life.

The EQ-5D consists of 5 items describing health state and the EuroQoL visual analog scale (VAS) of self-rated overall health. Responses for the 5 descriptive items are converted into a single index value or utility score according to EQ-5D scoring algorithm ranging from -1 to 1 where lower scores indicate worse health status. Utility scores will be calculated using the UK weighting algorithm. EQ-5D-VAS responses range from 0 (the worst health you can imagine) to 100 (the best health you can imagine).

For purposes of determining whether patients have experienced a clinically meaningful change in a given score, the following thresholds for minimum important difference (MID) will be used:

Scale/Sub-Scale	Threshold for definition of worsening or improvement
FACT-Leu Total Score	6
FACT-G (General) Scale	4
FACT-Leu TOI	4
Physical Well-Being (PWB)	2
Social/Family Well-Being (SWB)	2
Emotional Well-Being (EWB)	2
Functional Well-Being (FWB)	2
Leukemia Symptoms/concerns (LeuS)	3
EQ-5D-5L Utility (UK weight)	0.08
EQ-5D-5L VAS	7

Change thresholds for the FACT-Leu scales selected from ranges provided by (Whiteley, 2016).

Change thresholds for EQ-5D-5L scores from (Pickard, 2007; McClure 2017).

PRO Completion

Patient completion of each PRO instrument will be summarized as a percentage (number of completed out of number expected) at each collection time point by dose group.

Patient completion will be summarized using the following categories:

- All questions completed
- At least 50% completed

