- At least one question completed

(Note: Items noted as ‘optional’ in the instrument, specifically item GS7 “I am satisfied with my sex life” will not be considered missing for purposes of tabulating PRO completion.)

PRO Overall Instrument Scores

PRO total scores will include the FACT-Leu Total, FACT-Leu TOI, FACT-G, EQ-5D-5L Utility Score, and EQ-5D-5L VAS. (The EQ-5D-5L VAS is a single item but will be categorized with the overall instrument scores as it represents the concept of overall health status.)

For each overall instrument score, a table of descriptive statistics will be presented including mean, standard deviation, median, minimum and maximum at each time point and change from baseline for each post-baseline assessment, by dose group. Each overall instrument score will also be shown in line graphs of mean score and mean change from baseline by dose groups, with 95% CI.

PRO Domain Scores

PRO domain scores will include the FACT-PWB, FACT-FWB, FACT-EWB, FACT-SWB, and FACT-LeuS.

For each instrument domain score, a table of descriptive statistics will be presented including mean, standard deviation, median, minimum, and maximum at each time point and change from baseline for each post-baseline assessment, by dose group. Each overall instrument score will be shown in line graphs of mean score and mean change from baseline by dose groups, with 95% CI.

PRO Item Analyses

Selected individual items from the FACT-Leu addressing concepts of particular interest in the current study context of use will also be described in terms of their category responses. Specifically:

Item number	Item text
GP1	“I have lack of energy”
GP2	“I have nausea”
GP4	“I have pain”
GP5	“I am bothered by the side effects of treatment”
GP6	“I feel ill”
GF1	“I am able to work (including work at home)”

BRM3	“I am bothered by fevers (episodes of high body temperature)”
P2	“I have certain parts of my body where I experience pain”
An7	“I am able to do my usual activities”

For each item, a bar chart will show the distribution of responses (including missing responses), and a second bar chart will show the distribution of change in response categories from baseline (including missing responses).

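### The SAP's baseline cut-off at randomisation can leave participants without a PRO baseline, and the protocol's mixed-model and MID-based PRO analyses are missing from the SAP without a recorded reason

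*Protocol*

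**What the plan says.** **Baseline.** SAP 2.3: "Study Day 1 is the day of randomization for participants randomized in Part 1". SAP 2.4: "Baseline value is defined as the last non-missing value collected on or before study Day 1". Neither section makes an exception for PROs, and SAP 6 defines no baseline of its own.

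**Schedule.** Protocol Table 1 places randomisation within 72 hours of first dose. FACT-Leu and EQ-5D-5L have no entry under screening or randomisation. They start on Day 1 of each cycle, before dosing where possible, and are repeated at end of treatment and at the first follow-up visit.

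**Protocol analyses (9.4.3).** There are three layers. Descriptive statistics are planned at each visit, "for change from baseline at each time point, and for change from previous time point". For the longitudinal analysis, "Mixed-model repeated measures will be used for longitudinal analyses of PRO score change over time for each subscale". Kaplan-Meier analyses are added, "using specified MID thresholds to define time-to-worsening and time-to-improvement for each PRO scale score".

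**SAP analyses (section 6).** For the scores, "a table of descriptive statistics will be presented including mean, standard deviation, median, minimum and maximum at each time point and change from baseline", by dose group, with line graphs of mean score and mean change. Completion rates and bar charts for selected items are also planned. On thresholds, "the following thresholds for minimum important difference (MID) will be used", followed by values for ten scales.

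**Stated changes (SAP 1.6).** Part 2 did not proceed, and Part 1 results are to be descriptive, with no formal comparison and no test. PRO analyses are not mentioned.

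**The concern.** Protocol 4.2 gives the PRO data a purpose: to describe how symptoms and quality of life change over treatment, and possibly to inform dose tolerability. Change needs a starting value. For laboratory tests or ECOG status a screening result can serve if Day 1 falls after randomisation. For the two PRO instruments nothing is scheduled earlier, so the general baseline rule can leave a participant with no reference value at all.

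The second issue is traceability. The protocol commits to two PRO analyses that the SAP does not contain, and the SAP lists thresholds whose natural use was one of those analyses. A reader of the study report could not tell whether they were dropped deliberately or overlooked.

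At stake is the credibility of the quality-of-life results, not the primary endpoint.

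**Working it through.** The documents state no PRO sample size, power or bias figure, so there is nothing to reproduce. The check compares texts and adds one illustration.

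**1. Baseline rule against the schedule.** Let g be the number of calendar days from randomisation to Cycle 1 Day 1. A 72-hour window allows g = 0 to 3.

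- g = 0: the Cycle 1 Day 1 PRO falls on SAP Study Day 1 and counts as baseline.
- g ≥ 1: the first PRO falls after Study Day 1. No PRO baseline exists and no change score can be formed.

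If s is the share with g ≥ 1, the number per group with a PRO baseline is at most 50 × (1 − s):

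| s | Participants with a PRO baseline, per group |
|---|---|
| 0% | 50 |
| 50% | 25 |
| 100% | 0 |

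The documents do not give s. The table assumes full groups of 50 and a completed Cycle 1 Day 1 questionnaire. With a last-before-first-dose rule, everyone who completed that questionnaire before dosing has a baseline, whatever s is.

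The outputs affected are the change-from-baseline tables, the graphs of mean change and the item charts of change in response category. A mixed model of change and a time to worsening also need a reference score, so restoring them without correcting the baseline would not be enough.

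**2. Protocol against SAP.**

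| Analysis | Protocol 9.4.3 | SAP 6 |
|---|---|---|
| Visit descriptives and change from baseline | Yes | Yes |
| Mixed model for each subscale | Yes | Absent |
| Kaplan-Meier time to worsening and improvement by MID | Yes | Absent |
| MID values | Left to the SAP (8.9) | Ten listed, no named output applies them |

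SAP 1.6 does not settle the matter. Its descriptive-only statement does not exclude Kaplan-Meier summaries, because SAP 4.2.1.2, 4.2.1.3, 4.2.1.5 and 4.2.1.6 keep them for time to response, duration of response, PFS and OS. Nor does it exclude a mixed model used only for estimation.

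**3. Why losing the change score matters (illustration).** All inputs are assumptions: FACT-Leu SD of 20 or 30, a linear true decline to about −6 at the sixth post-baseline visit (the SAP's MID for the total score), 30% or 60% dropout by then, and low scorers more likely to leave. Per-visit dropout is 1 − (1 − d)^(1/6), which is 5.8% for d = 0.3 and 14.2% for d = 0.6. Each scenario simulated 20,000 participants. The mixed model was represented by maximum likelihood through sequential regression, without covariates.

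| SD | Dropout | Dropout driven by | True change | Difference of raw visit means | Mean paired change in those observed | Mixed-model type |
|---|---|---|---|---|---|---|
| 20 | 30% | previous observed score | −6.10 | −0.96 | −6.24 | −6.16 |
| 20 | 30% | unseen current score | −6.15 | −0.75 | −5.96 | −5.63 |
| 20 | 60% | previous observed score | −6.01 | +5.35 | −6.10 | −5.89 |
| 20 | 60% | unseen current score | −5.93 | +5.59 | −5.30 | −4.58 |
| 30 | 30% | previous observed score | −6.26 | +1.39 | −6.66 | −6.44 |
| 30 | 30% | unseen current score | −5.86 | +1.82 | −5.70 | −5.27 |
| 30 | 60% | previous observed score | −5.86 | +11.07 | −6.24 | −5.96 |
| 30 | 60% | unseen current score | −5.78 | +11.57 | −4.95 | −3.75 |

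In these scenarios the comparison of raw visit means hides or reverses a real decline, while within-participant change stays close to it. The mixed model is accurate when dropout follows observed scores and drifts when it does not. These figures rank the summaries under assumptions. They do not forecast bias in this trial.

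**The case against.** The case for the SAP is substantial. The visit descriptives were in the protocol from the start, so a reader who infers that the SAP substitutes them for the model goes too far: the SAP keeps one layer and omits two. Section 6 also plans within-participant change, so a sicker participant leaving does not by itself create apparent improvement in the planned change results. A reader might infer that quality of life will be seen only in survivors still on treatment. That fits the by-cycle means, but PROs are also scheduled at end of treatment and first follow-up, and completion is tabulated against the number expected, so attrition is visible though not adjusted for. Participants dosed on the day of randomisation keep their baseline.

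The protocol calls its statistical section general and leaves details to the SAP, and SAP 1.6 gives a descriptive-only context. The thresholds also have a stated purpose, judging whether change is clinically meaningful; what is missing is an output. Finally, a mixed model is no cure. It assumes dropout is explained by observed scores and does not resolve truncation by death.

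All of this stands as a limit on the point. None of it supplies a PRO baseline for a participant dosed after the randomisation date, and leaving details to a SAP does not amount to recording that a planned analysis was dropped.

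**Conclusion.** The point holds in two parts. First, the written baseline rule does not fit the PRO schedule. It removes all change-from-baseline results for anyone dosed on a later date than randomisation, a share anywhere from 0% to 100%. This is the more damaging part, because it takes away the more robust of the two score summaries the SAP plans. Second, two analyses committed to in the protocol are absent from the SAP without record, and ten MIDs are listed that no named output applies.

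A reader might try to express the dropout bias in FACT-Leu points by multiplying a share missing by a gap between leavers and stayers, and set the result against the MID of 6. The documents give neither input. That product also describes a mean level, whereas the MID is a threshold for change, so no such figure is offered here.

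PROs are exploratory, no hypothesis or formal decision criterion rests on them, and the complete response result is unaffected. The corrections are worth making because they cost little.

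**What to change.** 1. In SAP 2.4 or 6, define PRO baseline as the last assessment before first dose, on or before Cycle 1 Day 1. This is one line, needs no new data, and should be done first because the other analyses depend on it.
2. In SAP 6, restore the protocol's mixed model for each subscale, for estimation only. State its terms, since the protocol names none, and state that it assumes dropout is explained by observed scores and does not resolve truncation by death.
3. Restore the Kaplan-Meier time to worsening and time to improvement using the listed MIDs, with a stated rule for death. Keep the visit tables and completion rates as support.
4. If items 2 and 3 are not wanted, record and justify their removal in SAP 1.6 and name the output that uses the MIDs.

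Items 2 and 3 cost modest programming on data already collected. Item 4 costs a paragraph.
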